7.2 Adverse Event Reporting

The Investigators are responsible for monitoring the safety of patients who have been enrolled in this study. All AEs considered to be related to study treatment will be followed until the event resolves or has reached a fatal outcome. Adverse events will be evaluated for severity and graded following the Common Terminology Criteria for Adverse Events (CTCAE) version 4.0 as follows: Grade 1 (mild)- asymptomatic or mild symptoms; intervention not indicated, Grade 2 (moderate)- minimal symptoms; local or noninvasive intervention indicated, Grade 3 (severe)- medically significant but not immediately life threatening; hospitalization or prolonged hospitalization indicated, Grade 4 (life-threatening)- urgent intervention indicated, Grade 5- death related to AE.

The principle investigator will determine with attribution of each AE. AEs will be categorized into one of five classes: definite- clearly related to ____, probable- likely related to ____, possible- may be related to ____, unlikely- doubtfully related to ____, or unrelated- clearly not related to ____.

Attempts will be made to identify what the AE is related to and not merely what it is not related to.

The Investigators will document all AEs occurring during the study, commencing with the date of PAE treatment and including the protocol-defined post treatment follow-up period (21 CRF §312.64[b]), which is defined as 12 months post date of PAE, on the AE CRF. AEs and SAEs that occur following the signature of informed consent but prior to treatment will not be captured or reported.

The protocol will be terminated following the first occurrence of a serious adverse event, specifically nontarget pelvic embolization or procedure-related death.

7.3 Reporting Serious Adverse Events

Any unanticipated adverse event or SAE, including death due to any cause that occurs during the study treatment or initial 12 month follow-up period, whether or not related to the study treatments, will be reported to the FDA within 3 days of the site learning of the event. The SAE form must be completely described on the AE CRF as well as the Serious Adverse Event form. Specifically, any bladder or rectal injuries will be reported to the IRB and FDA immediately.

Safety Contact Information:

[name]
UCSD Department of Radiology
[name]
[name]

[contact]
[contact]
Email: [contact]

8. Symptom Assessments

8.1 International Prostate Symptom Score (IPSS)

The IPSS is a validated 8-question tool that is self-administered by the patient, and evaluates symptoms (7 questions) and quality of life (1 question). A copy of the IPSS can be found in Appendix D.

8.2 International Index of Erectile Function (IIEF)

The IIEF is a validated 15-question tool that is self-administered by the patient, and evaluates male sexual function, sexual desire and intercourse satisfaction. A copy of the IIEF questionnaire can be found in Appendix E.

9. Statistical Analysis

9.1 General Considerations

In general, continuous variables will be summarized as n, mean, standard deviation, median, minimum and maximum. Categorical variables will be summarized as the number and percentage of patients in each category.

Data listings will include all data collected on the case report forms (CRFs), as well as any derived variables (study day, age, etc.). Data collected on patients who are screen failures will not be included in any summary tables, listings or analyses.

For each parameter, baseline is defined as the value reported prior to the study procedure. If multiple values were collected prior to the procedure, the value closest to the date/time of the initiation of the procedure will be used as baseline. This may include values collected earlier in the day on the date of the procedure.

Unscheduled data, such as information from unscheduled visits, repeat laboratory tests, or Investigator comments will be excluded from data listings and summary tables unless otherwise specified (such as data collected on adverse events). Any outliers detected during the review of the data will be investigated. If necessary, the data will be queried and corrected in the database prior to database lock and the generation of the final tables and listings.

All primary and secondary analyses will be performed on a locked database after all patients have completed the 12-month follow-up of the investigation or been lost to follow-up. Data from the long term follow-up period will be analyzed separately.

Analyses will be performed using SPSS, version 22 or higher.

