3.1 Inclusion Criteria

Patients must meet all of the following inclusion criteria in order to be eligible for this study.

1. Provided informed consent
2. Age greater than 50 years and less than 85 years
3. Prostate volume between 40 and 300 cm³
4. Diagnosis of BPH with moderate to severe lower urinary tract symptoms (LUTS) defined as at least one of the following:
 - a. IPSS greater than 18
 - b. IPSS Quality of Life (QoL) assessment greater than 3
 - c. Qmax less than 12 mL/sec
5. Refractory or intolerant to medical management
6. Ineligibility for or refusal of surgical management
7. One of the following criteria:
 - a. Baseline prostate specific antigen (PSA) ≤ 2.5 ng/mL
 - b. Baseline PSA > 2.5 ng/mL and ≤ 10 ng/mL AND free PSA $\geq 25\%$ of total PSA
 - c. Baseline PSA > 2.5 ng/mL and ≤ 10 ng/mL AND free PSA $< 25\%$ of total PSA AND negative 12 core prostate biopsy in the past 12 months
 - d. Baseline PSA > 10 ng/mL AND negative 12 core biopsy within the past 12 months

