This is a phase I/II, single center, prospective, single arm, investigational study to evaluate the safety and efficacy of prostate artery embolization (PAE) for treatment of severe lower urinary tract symptoms (LUTS) related to benign prostatic hyperplasia (BPH) in patients with prostate size between 40 and 300 cm³ that have either failed or are intolerant to medical management. Patients will be considered enrolled in the study once they have provided informed consent. A total of 20 patients will be enrolled in the single treatment arm of the study. Treated participants will be followed for no less than 24 months.

The study will involve a screening period in which patient eligibility is determined. Once eligibility is confirmed, patients will undergo PAE with Embosphere Microspheres within 4 weeks of baseline prostate ultrasound. Following treatment, patients will return for follow-up visits at 1, 6, 12, and 24 months post PAE. At each of these visits, patients will complete the International Prostate Symptom Score (IPSS) and International Index of Erectile Function (IIEF) questionnaires, undergo a physical exam, transrectal prostate ultrasound, transabdominal prostate ultrasound, uroflowmetry and laboratory evaluations, and medication and adverse event reviews.

The primary objective of the study will be improvement of BPH symptoms as assessed by the IPSS questionnaire. Patients will continue to be followed according to the institutional standard of care follow-up schedule after they complete the study.

Safety will be evaluated throughout the study by assessing adverse events and findings on physical examination. Concomitant medication usage will also be assessed.

5. Treatments and Assessments

Study participants will be treated with a single PAE procedure performed with Embosphere Microspheres. The microspheres will be mixed with a contrast agent and will be delivered to the arteries supplying the prostate via a microcatheter. The occlusion endpoint will be stasis as defined as persistent contrast in the feeding vessel that persists for 5 heartbeats. A complete description of the technical protocol to be followed is provided in Appendix C.

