9.2 Sample Size Calculations

This is a phase I/II, single center, prospective, single arm, investigational study to evaluate the safety and efficacy of prostate artery embolization (PAE) for treatment of severe LUTS related to BPH in patients with prostate size between 40 and 300 cm³ that have either failed or are intolerant to medical management. Twenty patients treated with PAE with Embosphere Microspheres are considered sufficient to provide data that will be used to evaluate the study objectives. No formal sample size calculations have been performed.

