9.5.1 International Prostate Symptom Score (IPSS)

The primary efficacy outcome will be based on the IPSS. The IPSS is a frequent used, validated, 8 item (7 symptom burden questions and 1 quality of life question) instrument which can be serially performed to compare the progression of symptoms and their severity over months and years. Patients are asked to assess how often they have experienced the following 7 symptoms in the past month: incomplete emptying, frequency, intermittency, urgency, weak urine stream, straining and nocturia. The response categories range from 0=Not at all to 5=Almost always. The total IPSS score is calculated by summing the responses for the 7 symptom burden items. The eighth item is an assessment of patient quality of life due to LUTS and does not contribute to the IPSS score calculation.

Patients will be classified into one of 3 symptom severity categories based on their total IPSS score as follows:

- Mildly symptomatic: 0-7
- Moderately symptomatic: 8-19
- Severely symptomatic: 20-35

The IPSS total score will be summarized for the baseline, 1 month, 6 month and 12 month time points, including change from baseline. Change from baseline will be calculated as post baseline IPSS score minus baseline IPSS score. A negative value indicates symptom improvement. 95% confidence intervals will be calculated for the mean change from baseline to the post baseline time points. For informational purposes, IPSS scores will also be summarized separately for patients that receive unilateral and bilateral PAE if there are sufficient numbers in both groups.

The primary efficacy analysis will be the change in IPSS total score from baseline to 12 months post PAE for the ITT population. A Paired-Sample Wilcoxon Signed Rank Test will be used to assess the statistical significance of the change from baseline to 12 months post PAE. A secondary analysis of the proportion of patients who have improved by at least one IPSS symptom category (i.e., severe to moderate, severe to mild, or moderate to mild) from baseline to 12 months post PAE will also be performed. A 95% confidence interval will be calculated for the proportion. The proportion of patients improving at least 3 points on the IPSS total score at the 12 month time point will also be summarized and the corresponding 95% confidence interval will be calculated.

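### For men admitted on IPSS >18, the qualifying score is also the baseline, so some regression to the mean counts as improvement in the uncontrolled primary analysis

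*Combined protocol and SAP*

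**What the plan says.** Inclusion criterion 4 (Section 3.1) requires moderate to severe symptoms, "defined as at least one of the following": "IPSS greater than 18", an IPSS quality-of-life score above 3, or Qmax below 12 mL/sec.

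Visit -1 (Section 5.1) is a combined screening and baseline visit within 4 weeks of PAE, and the IPSS is completed there. Neither the Visit 1 list (Section 5.2) nor the Day 1 column of Appendix A contains an IPSS.

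Section 9.1 states that "baseline is defined as the value reported prior to the study procedure". If there are several such values, "the value closest to the date/time of the initiation of the procedure will be used as baseline", and values from the procedure day are allowed. The same section leaves data from unscheduled visits out of listings and summary tables unless otherwise specified.

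Section 4 describes the design: "This is a phase I/II, single center, prospective, single arm, investigational study". "A total of 20 patients will be enrolled in the single treatment arm of the study". Section 9.5.1 makes the change in IPSS total from baseline to 12 months in the ITT population the primary analysis: "A Paired-Sample Wilcoxon Signed Rank Test will be used to assess the statistical significance of the change from baseline to 12 months post PAE". The QoL item is reported as change from baseline with confidence intervals. Section 9.2 adds: "No formal sample size calculations have been performed".

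**The concern.** Men chosen because one reading was high will, on average, read lower next time even if nothing is done. Where the reading that admits a man is also the value from which his change is measured, that fall goes straight into the change score. A concurrent control would show the same fall and cancel it, but this study has none. The signed rank test compares the change with zero, so it cannot separate a selection effect from a treatment effect. The error runs one way, toward apparent benefit, and it also touches the 3-point and category-improvement proportions in Section 9.5.1. The documents mention no run-in, repeat baseline or adjustment.

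The QoL item has the same structure for men who enter on QoL >3.

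**Working it through.** The plan gives no figure to reproduce: it states no alpha, SD, effect size or test-retest correlation.

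**Inputs from the documents.** n = 20; cut-off IPSS >18 (19 or more, so 18.5 with continuity correction); any one of three routes suffices; paired Wilcoxon test against zero.

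**Assumptions, none in the documents.** Screened IPSS mean m = 18 to 22; SD s = 7; correlation r = 0.7 to 0.9 between the screening and 12-month scores; a share q of screened men who meet the QoL or Qmax route whatever their IPSS; no true effect; two-sided 0.05, so 2.5% nominal for false improvement.

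**Mean bias.** With a = (18.5 - m)/s, P = 1 - Φ(a) and the other routes independent of IPSS:

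spurious change = -(1 - r) × s × φ(a) × (1 - q) / [P + q(1 - P)]

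- For m = 18: a = 0.071, φ = 0.398, P = 0.472.
- For m = 22: a = -0.5, φ = 0.352, P = 0.691.
- q = 0.5, m = 18, r = 0.7: 0.3 × 7 × 0.398 × 0.5 = 0.418; 0.418 / (0.472 + 0.5 × 0.528) = 0.418/0.736, giving -0.57.
- q = 0.5, m = 22, r = 0.9: 0.1 × 7 × 0.352 × 0.5 = 0.123; 0.123/0.846, giving -0.15.
- q = 0.75, m = 18, r = 0.7: 0.209/0.868, giving -0.24.
- q = 0.9, m = 22, r = 0.9: 0.0246/0.969, giving -0.03.
- q = 0, m = 18, r = 0.7: 0.836/0.472, giving -1.77.
- q = 0, m = 22, r = 0.9: 0.246/0.691, giving -0.36.

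**Error rate.** Simulated trials of 20 men, with scores rounded and bounded at 0 to 35, agree with these means and give:

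| Share also meeting another route | Spurious mean change | False significant improvement |
|---|---|---|
| 0 (IPSS alone admits) | -0.4 to -1.8 | 10 to 30%, about 7% at m = 22, r = 0.9 |
| 50% | -0.15 to -0.6 | 4 to 7% |
| 75 to 90% | -0.03 to -0.25 | 2 to 4% |

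**If the other routes are correlated with IPSS.** Independence is the favourable case. With correlation 0.5 between the other routes and the screening IPSS (SD 6.5, mean 16 to 23, r 0.6 to 0.8), the results are:

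- 85% meeting another route: -0.16 to -0.39 points, 3.4 to 4.9%.
- 60%: -0.34 to -0.99 points, 5 to 10%.
- 30%: -0.48 to -1.84 points, 7 to 28%.

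**Responder proportions, no effect, mean 20, r = 0.8, SD 7.** With IPSS-only entry, a fall of at least 3 points occurs in 35% of men, against 28% from a separate baseline with independent error. Category improvement occurs in about 18% against 11%.

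**Effect of a Day 1 score.** If its error is independent of the screening error, the mean spurious change is about zero and the error rate returns to about 2.5%. If half the error variance is shared, half the bias stays: 0.5 × -1.77 = -0.89 points at m = 18, r = 0.7 with IPSS-only entry, and false improvement is still about 10%.

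**The case against.** A reader might infer that every man is selected on his baseline IPSS, so that the primary test has a 10 to 30% chance of a false positive. The documents do not support that. Criterion 4 is met by any one of three routes, so a man with IPSS of 18 or less can enter on QoL or Qmax. The high rates belong to a trial in which IPSS alone admits everyone. These men are refractory to or intolerant of medical management (criterion 5), so it is plausible, though not shown, that most also meet QoL >3 or Qmax <12. This part of the objection stands.

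The likely bias is also small by the plan's own measures. A bias of 0.6 points is one fifth of the 3-point responder threshold, and about 9% (0.6/6.7) of the 6.7-point improvement quoted in the background, whose scale is not named. For an early 20-patient study with no stated alpha, this limits the consequence. It does not change the direction, and the correction is nearly free.

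A reader might also infer that a Day 1 IPSS removes the problem. That goes too far. The IPSS items look back about four weeks and screening falls within four weeks of PAE. If screening is 7 days before the procedure, 21 of the 28 recall days are shared, and a flare that raised the first score can raise the second. Nor does a repeat baseline deal with placebo response or with men seeking care when symptoms peak, both of which may be larger.

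**Conclusion.** The point holds for men admitted through IPSS >18, and for the QoL item in men admitted through QoL >3. One scheduled score serves as both qualifying value and baseline, and the uncontrolled change from it includes some regression to the mean, always toward improvement.

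Under the stated assumptions with independent routes, the effect is a fraction of a point and modest error inflation when half or more of screened men also meet another route. It would be larger if few men meet another route, if those routes track the IPSS closely, or if r is below 0.7. The documents do not give the SD, the correlation or the mix of qualifying routes, so the true size cannot be settled from them. The 10 to 30% rates, with up to -1.8 points, are a worst case and not an estimate for this trial. The change is a worthwhile cheap improvement; the study does not depend on it.

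**What to change.** 1. Add the IPSS, including the QoL item, to Visit 1 before the procedure, in Section 5.2 and in the Day 1 column of Appendix A. It must be a scheduled assessment, because Section 9.1 generally leaves unscheduled data out of the summaries.
2. State that the screening IPSS is for eligibility only. The closest-value rule in Section 9.1 then makes the Day 1 score the baseline without further change.
3. Record and report which part or parts of criterion 4 each man met, so that readers can see how many entered on IPSS alone.
4. Say in the report that overlapping recall may leave some of this bias, and that an uncontrolled change also contains placebo response and natural fluctuation.

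The cost is one 8-item self-completed form per man, 20 forms in all, at a visit he already attends. The reported improvement may be slightly smaller.

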9.2 Sample Size Calculations

This is a phase I/II, single center, prospective, single arm, investigational study to evaluate the safety and efficacy of prostate artery embolization (PAE) for treatment of severe LUTS related to BPH in patients with prostate size between 40 and 300 cm³ that have either failed or are intolerant to medical management. Twenty patients treated with PAE with Embosphere Microspheres are considered sufficient to provide data that will be used to evaluate the study objectives. No formal sample size calculations have been performed.

9.3 Analysis Populations

9.3.1 Intent-to-Treat Population

The Intent-to-Treat (ITT) Population is defined as all patients who undergo PAE with Embosphere Microspheres. This will be the primary population for all efficacy analyses.

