
The first United States trial published in 2013 and updated in 2014 reports the treatment of 20 patients with symptomatic BPH. 90% technical success and 95% clinical success was reported at 1 month with prostate volume decreased 18% at 3 months (14). There were no major complications. Minor complications include a mild self-limited post-embolization syndrome consisting of pain, nausea, and malaise. Self-limited hematuria, dysuria, urinary frequency, and pelvic pain have also been reported. Gao *et al* published a prospective randomized trial comparing PAE to TURP in 114 patients (15). Both procedures demonstrated significant clinical improvement. The PAE group had more clinical failures (9.4% vs 3.9%) but reduced procedural bleeding, less need for urethral catheterization, and shorter hospital stay.

Prostate artery embolization has been performed with nonspherical PVA particles (10,11,12,15), tris-acryl gelatin microspheres (9,13), and hydrogel microspheres with a proprietary coating (14). No studies have been performed to directly compare the efficacy of these embolic agents. At UC San Diego we frequently

use microspheres for procedures requiring arterial embolization. We are experienced with a wide range of embolic materials. We propose using 300-500 μm and 100-300 μm Embospheres (Merit Medical; South Jordan, UT) as the embolic agent in this study.

PAE for LUTS attributed to BPH provides a minimally invasive treatment option with several advantages compared to surgical therapy. Excellent technical and clinical success is reported. The procedure is minimally invasive and can be performed as an outpatient procedure with minimal pain. Side effects are mild and self-limited, and major complications are rare. PAE is a technically challenging procedure. The clinical success rate is reduced when only unilateral embolization is possible, and poor technique could result in nontarget embolization resulting in pain or pelvic organ dysfunction. Further investigation is necessary to determine the safety of this procedure, the appropriate indications, the ideal embolic material, the durability of effect, and to directly compare this technique with surgical management.

2. Study Objectives

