Appendix C: Technical Protocol for Prostate Artery Embolization

- Administer prophylactic IV antibiotics, based on institution standard of care. Choice of antibiotic and sedation will be at the discretion of the interventional radiologist.
- Prior to embolization, insert a Foley catheter into patient's bladder and fill it with a mixture of 50% contrast agent and 50% saline. This will provide a visual landmark during angiography.
- Local anesthesia should be administered for a transfemoral approach on the side with the best arterial pulse.
- Conduct pelvic angiography with a 5Fr catheter to evaluate aortoiliac vessels and prostate arteries during the arterial and late phases.
- Observe closely for vascular conditions and blood flow that might preclude catheter placement or embolic injection, including severe atheromatous disease, arteriovenous shunt, or presence of feeding arteries that are too small to accept the microspheres. If these conditions are present and a viable feeding artery without these problems cannot be identified, embolization will be conducted on the contralateral side of the prostate. If these conditions are present on both sides of the prostate, no embolization will be performed.
- If appropriate, anastomoses to non-targeted vessels and/or endangering collateral vessel pathways will be closed off with a larger size of embolic particles or embolic coils chosen to be appropriate to the size of the anastomosis or collateral vessel. If anastomoses or endangering collateral vessels cannot be closed off, the embolization will be performed only on the contralateral side of the prostate, if it is not affected by the condition. If anastomosis or endangering collateral vessels affects both sides of the prostate, no embolization will be performed.
- If vasospasm occurs, follow institution standard of care, which could include withdrawing the catheter slightly and waiting, or delivering a small amount of nitroglycerin. If the vasospasm cannot be resolved, conduct the embolization only on the contralateral side of the prostate.
- Ensure that the tip of the micro catheter is at or inside the ostium of the prostate arteries with additional angiography.
- Procedural endpoint is stasis of the terminal branches of the arteries feeding the prostate, while maintaining patency of the main artery branches.

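### The set labelled 'Intent-to-Treat' in Section 9.3.1 holds only men who receive microspheres, so the 12-month responder proportions and mean IPSS change are conditional on delivery of embolization

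*Combined protocol and SAP*

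**What the plan says.** Section 9.3.1 defines the Intent-to-Treat Population: "defined as all patients who undergo PAE with Embosphere Microspheres. This will be the primary population for all efficacy analyses". The Evaluable Population (9.3.2) starts from the same men, and the Safety Population (9.3.3) is stated to be identical to the ITT set.

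Section 4 (Study Design) places enrolment earlier: "Patients will be considered enrolled in the study once they have provided informed consent".

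Appendix C has two branches, both after femoral access and pelvic angiography, in which a man leaves without treatment. One covers vascular conditions that preclude catheter placement or injection: "If these conditions are present on both sides of the prostate, no embolization will be performed". The other covers vessels that cannot be closed off: "If anastomosis or endangering collateral vessels affects both sides of the prostate, no embolization will be performed".

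Section 9.5.1 plans the change in IPSS at 12 months (primary, Wilcoxon signed-rank) with a confidence interval for the mean change. It also plans two responder proportions with 95% CIs: improvement by at least one severity category, and improvement by at least 3 points. Men embolized on one side only remain in these analyses and are also summarized separately if numbers allow.

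Section 9.5.7 carries the baseline value forward, within the ITT analyses, for a man with no post-baseline data.

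**The concern.** A reader who sees Intent-to-Treat in a single-arm procedural study will assume that men taken to the procedure are in the denominator. Here a man can consent, pass screening, have arterial access and angiography, receive nothing, and appear in no efficacy result. The background section itself describes PAE as technically demanding, so this path is not remote.

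The plan is also uneven. Section 9.5.7 scores a treated man without follow-up as unimproved and presents that as conservative, while a man who could not be treated at all is left out of the denominator. Section 9 plans no delivery proportion, so a reader of the report could not reconstruct what was left out.

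At stake are the responder proportions, the mean change, and what the ITT label claims. This point concerns efficacy only, not the reporting of adverse events.

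**Working it through.** **No figure to reproduce.** Section 9.2 gives 20 patients and states "No formal sample size calculations have been performed". The check is a tracing exercise followed by an illustration.

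**Step 1: follow a man who is not embolized.**
- Section 4: he is enrolled at consent.
- Appendix C: access and angiography are done, one of the two branches applies, and no microspheres are given.
- 9.3.1 to 9.3.3: he is in none of the three populations.
- Section 4 describes follow-up for treated participants, and 9.5.7 describes listings and tables for treated patients. He has no planned 12-month IPSS.
- 9.5.7: the baseline-carried-forward rule operates within the ITT analyses, so it does not reach him.
- If he is instead classed as a screen failure, Section 9.1 removes him from all tables, listings and analyses.

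Every route leads to the same place: he has no efficacy value.

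**Step 2: effect on a responder proportion.** Let n be men attempted, m men not embolized and x responders. The plan reports x/(n − m). Counting non-embolized men as non-responders gives x/n. Take n = 20 and x = 15 (both illustrative), with exact Clopper-Pearson intervals:

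| m | Plan reports | All attempted | Difference |
|---|---|---|---|
| 0 | 15/20 = 75.0% (50.9 to 91.3%) | the same | 0 |
| 1 | 15/19 = 78.9% (54.4 to 93.9%) | 15/20 = 75.0% (50.9 to 91.3%) | 3.9 points |
| 2 | 15/18 = 83.3% (58.6 to 96.4%) | 15/20 = 75.0% (50.9 to 91.3%) | 8.3 points |

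**Step 3: effect on the mean change.** With change set to 0 for non-embolized men, the all-attempted mean is the treated mean × (n − m)/n. An assumed −10 becomes −10 × 19/20 = −9.5 for m = 1 and −10 × 18/20 = −9.0 for m = 2.

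**Step 4: how likely is m ≥ 1?** The documents give no rate for this agent. For assumed non-delivery rates among 20 attempts:
- 5%: P(m ≥ 1) = 1 − 0.95^20 = 0.64.
- 10%: P(m ≥ 1) = 1 − 0.90^20 = 0.88, and P(m ≥ 2) = 0.61.

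**Step 5: what 20 counts.** Section 4 says "A total of 20 patients will be enrolled in the single treatment arm of the study", whereas Section 9.2 says "Twenty patients treated with PAE with Embosphere Microspheres are considered sufficient". If 20 means treated men and 2 further men are not embolized, there are 22 attempts, and 15/20 = 75.0% becomes 15/22 = 68.2% (45.1 to 86.1%). The documents do not say whether a non-embolized man counts towards 20.

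**Step 6: the primary test.** The usual form of the Wilcoxon signed-rank test drops zero differences. Adding men with change 0 would therefore normally leave the p-value as it was.

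**The case against.** The strongest reply is that a treated set is what the study wants. The primary objective (2.1) concerns IPSS after PAE with these microspheres, and 9.3.1 states its definition openly. That stands: the set is legitimate and may remain primary. The label does not fit it, and the complementary result is missing.

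A second reply is that such men are screened out. CT angiography at screening (5.1) and exclusions 8 and 9 overlap with the Appendix C branches. This will lower the number. It does not bring it to zero, because arteriovenous shunts and feeding arteries too small for the microspheres are not listed exclusions, and Appendix C still provides for men who reach angiography. It does affect the remedy: a population restricted to eligible men could lose these cases again through exclusions 8 and 9.

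Third, the results are imprecise and no success threshold is set. An 8-point shift lies within intervals about 38 to 40 points wide. That is true, but the shift is systematic and the intervals do not account for it.

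Three stronger readings are tempting and not supported:
- A reader might infer that the rates are conditional on technical success. The documents do not define that term, and unilateral cases stay in. The condition is delivery of any microspheres.
- A reader might take the background figure, "90% technical success and 95% clinical success was reported at 1 month", to mean that 10% will go untreated. It comes from another trial with a different embolic agent. If both percentages refer to the 20 men in that trial, 19 clinical successes exceed 18 technical successes, so at least one technical failure improved. That sits badly with equating technical failure with no embolization, although the denominators are not given.
- A reader might infer that the bias can only favour the procedure. For the responder proportions this holds once non-embolized men are scored as non-responders. Their actual 12-month IPSS is unknown, because no follow-up is planned for them.

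**Conclusion.** The point holds as one of labelling and of a missing complementary analysis. The set named Intent-to-Treat is a treated set, and men whose procedure is started without delivery are counted in no efficacy result. The responder proportions and the mean change can therefore overstate the result for men taken to the procedure, by about 4 points with one such man in 20 and about 8 points with two, if 15 men respond. These sizes rest on assumed numbers of attempts, responders and non-deliveries, and on scoring non-embolized men as unimproved. If every man is embolized, nothing changes. The documents do not support a claim that the primary p-value is compromised. The change should be made, and made before database lock, so that the choice is not post hoc.

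**What to change.** 1. In 9.3.1, rename the present set 'Treated Population'. It may stay primary.
2. Add an 'All-Attempted Population': all enrolled men in whom arterial access for PAE was obtained, whether or not exclusion 8 or 9 is then found at angiography. State in 9.1 that these men are not screen failures.
3. In 9.5.1, report both 12-month responder proportions with 95% CIs in this population, counting non-embolized men as non-responders. Report the mean IPSS change with their change set to 0, stated as an assumption.
4. Report the delivery proportion (bilateral, unilateral, none) with a 95% CI.
5. Reconcile Sections 4 and 9.2 on whether 20 counts enrolled or treated men, and say whether a man who is not embolized counts towards it.

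The cost is SAP wording, one extra column in the responder table, and a record of each started procedure and its delivery outcome. No extra visits are needed, because non-embolized men are scored by rule. The downside for the sponsor is a slightly less favourable responder rate.
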